6.5 CONCOMITANT THERAPY

Any medication or vaccine (including over-the-counter or prescription medicines, vitamins, and/or herbal supplements) that the participant is receiving at the time of enrollment or receives during the study must be recorded along with:

- Reason for use.
- Dates of administration including start and end dates.
- Dosage information including dose and frequency.

Participants must abstain from taking prohibited prescription drugs within 7 days (or 14 days if the drug is a potential enzyme inducer) or 5 half-lives (whichever is longer) before the start of study intervention until completion of the follow-up visit, unless, in the opinion of the Investigator and Sponsor, the medication will not interfere with the study.

Paracetamol/acetaminophen, at doses of ≤ 2 grams/day, is permitted for use any time during the study. Other concomitant medication may be considered on a case-by-case basis by the Investigator in consultation with the Medical Monitor, if required.

Cetaphil, Vanicream, or the preferred same moisturizer not containing additives will be dispensed by the study site and its use is allowed on all body areas except the targeted assessment areas. No moisturizers or emollients are allowed at any time during the study for the targeted lesional and non-lesional skin areas including a buffer zone of 5 cm in AD patients and the targeted skin areas in HV for TEWL assessments from Day -7 to Day 113 (Week 16, EoT).

6.5.1 Rescue medicine

If absolutely medically necessary (ie, to control intolerable AD symptoms on face and genital areas), rescue treatment for AD may be provided to study patients at the discretion of the investigator. Investigators should make every attempt to conduct efficacy and safety assessments (eg, disease severity scores, safety labs) immediately before administering any rescue treatment. An unscheduled visit may be used for this, if necessary.

6.5.1.1 Prohibited medications and procedures

Treatment with the following concomitant medications and procedures is prohibited until the EoT visit:

1. Medications used for the treatment of AD or for super-infection:
 - Topical calcineurin inhibitors (tacrolimus or pimecrolimus)
 - Topical phosphodiesterase inhibitors (crisaborole)
 - Topical corticosteroids
2. Topical antibiotics
3. Vitamins and dietary or herbal supplements (unless approved by the investigator)
4. Use of any moisturizers other than those approved and dispensed by the study staff.
5. Systemic treatment for AD with an immunosuppressive/immunomodulating agent (including, but not limited to, systemic corticosteroids, CsA, AZA, MTX, MMF, IFN- γ , or other biologics)
6. Treatment with immune modulating biologics including, but not limited to, the following:
 - Any cell-depleting agents (eg, rituximab)
 - Infliximab, adalimumab, golimumab, certolizumab pegol, abatacept, etanercept, or anakinra
7. Procedures used for the treatment of AD (these are considered rescue procedures):
 - Phototherapy (such as ultraviolet B (UVB), narrowband UVB (NBUVB), ultraviolet A1 (UVA1), or psoralen-UVA (PUVA))
 - Bleach baths
 - Use of a tanning booth/parlor
8. In addition, participants will be asked to abstain from live (attenuated) vaccinations through Week 16. If a participant requires a vaccination prior to 16 weeks after

discontinuing treatment with dupilumab, titers should be checked post-vaccination. Live (attenuated) vaccinations include but are not limited to the following:

- Bacillus Calmette-Guérin (BCG)
 - Chickenpox (Varicella)
 - FluMist-Influenza
 - Intranasal influenza
 - Measles (Rubeola)
 - Measles-mumps-rubella (MMR) combination
 - Measles-mumps-rubella-varicella (MMRV) combination
 - Mumps
 - Oral polio (Sabin)
 - Oral typhoid
 - Rotavirus
 - Rubella
 - Smallpox (Vaccinia)
 - Varicella Zoster (shingles)
 - Yellow fever
9. Taking showers or soaking in a bathtub with soaps and body washes within 6 hours before TEWL assessments is to be avoided. Moisturizers other than Cetaphil, Vanicream, or the preferred same moisturizer not containing additives are prohibited.

6.5.1.2 Permitted medications

Other than the prohibited medications and procedures listed in [Section 6.5.1.1](#), treatment with concomitant medications and procedures is permitted during the study. This includes treatment with contraceptives, nasal and inhaled corticosteroids, and oral antihistamines.

6.6 DOSE MODIFICATION

No change in IMP dose is allowed.

6.7 INTERVENTION AFTER THE END OF THE STUDY

Any intervention after the EOS Visit will be at the discretion of investigator or treating physician.

7 DISCONTINUATION OF STUDY INTERVENTION AND PARTICIPANT DISCONTINUATION/WITHDRAWAL

7.1 DISCONTINUATION OF STUDY INTERVENTION

7.1.1 Definitive discontinuation

In rare instances, it may be necessary for a participant to permanently discontinue (definitive discontinuation) study intervention. If study intervention is definitively discontinued, the participant will remain in the study to be evaluated for TEWL, lipidomics, proteomics and transcriptomics. See the SoA for data to be collected at the time of discontinuation of study intervention and follow-up and for any further evaluations that need to be completed.

Pregnancy in a female participant will lead to definitive intervention discontinuation in all cases.

Handling of participants after definitive intervention discontinuation

Participants will be followed-up according to the study procedures specified in this protocol up to the scheduled date of study completion, or up to recovery or stabilization of any AE to be followed-up as specified in this protocol, whichever comes last.

If possible, and after the definitive discontinuation of intervention, the participants will be assessed using the procedure normally planned for the last dosing day with the IMP.

All cases of definitive intervention discontinuation must be recorded by the Investigator in the appropriate pages of the e-CRF when considered as confirmed.

7.1.2 Temporary discontinuation

Temporary intervention discontinuation may be considered by the Investigator because of suspected AEs. For all temporary intervention discontinuations, duration should be recorded by the Investigator in the appropriate pages of the eCRF.

The following definition can be considered:

Eg, temporary intervention discontinuation decided by the Investigator corresponds to one dose not administered to the participant.

7.2 PARTICIPANT DISCONTINUATION/WITHDRAWAL FROM THE STUDY

- A participant may withdraw from the study at any time at his/her own request, or may be withdrawn at any time at the discretion of the Investigator for safety, behavioral, compliance, or administrative reasons. This is expected to be uncommon.
- At the time of discontinuing from the study, if possible, an early discontinuation visit should be conducted, as shown in the SoA. See SoA for data to be collected at the time of

study discontinuation and follow-up and for any further evaluations that need to be completed.

- The participant will be permanently discontinued both from the study intervention and from the study at that time.
- If the participant withdraws consent for disclosure of future information, the Sponsor may retain and continue to use any data collected before such a withdrawal of consent.
- If a participant withdraws from the study, he/she may request destruction of any samples taken and not tested, and the Investigator must document this in the site study records.

If participants no longer wish to take the IMP, they will be encouraged to remain in the study.

The Investigators should discuss with them key visits to attend. The value of all their study data collected during their continued involvement will be emphasized as important to the public health value of the study.

Participants who withdraw from the study intervention should be explicitly asked about the contribution of possible AEs to their decision, and any AE information elicited must be documented.

All study withdrawals should be recorded by the Investigator in the appropriate screens of the e-CRF and in the participant's medical records. In the medical record, at least the date of the withdrawal and the reason should be documented.

In addition, a participant may withdraw his/her consent to stop participating in the study. Withdrawal of consent for intervention should be distinguished from withdrawal of consent for follow-up visits and from withdrawal of consent for non-participant contact follow-up, eg, medical record checks. The site should document any case of withdrawal of consent.

Participants who have withdrawn from the study cannot be reallocated (treated) in the study. Their inclusion and intervention numbers must not be reused.

7.3 LOST TO FOLLOW UP

A participant will be considered lost to follow-up if he or she repeatedly fails to return for scheduled visits and is unable to be contacted by the study site.

The following actions must be taken if a participant fails to return to the clinic for a required study visit:

- The site must attempt to contact the participant and reschedule the missed visit as soon as possible and counsel the participant on the importance of maintaining the assigned visit schedule and ascertain whether or not the participant wishes to and/or should continue in the study.
- Before a participant is deemed lost to follow up, the Investigator or designee must make every effort to regain contact with the participant (where possible, 3 telephone calls and, if

necessary, a certified letter to the participant's last known mailing address or local equivalent methods). These contact attempts should be documented in the participant's medical record.

- Should the participant continue to be unreachable, he/she will be considered to have withdrawn from the study.

8 STUDY ASSESSMENTS AND PROCEDURES

- Study procedures and their timing are summarized in the SoA, [Section 1.3](#) and [Section 1.4](#). Protocol waivers or exemptions are not allowed.
- Adherence to the study design requirements, including those specified in the SoA, is essential and required for study conduct.
- All screening evaluations must be completed and reviewed to confirm that potential participants meet all eligibility criteria. The Investigator will maintain a screening log to record details of all participants screened and to confirm eligibility or record reasons for screening failure, as applicable.
- Procedures conducted as part of the participant's routine clinical management (eg, blood count) and obtained before signing of the ICF may be utilized for screening or baseline purposes provided the procedures met the protocol-specified criteria and were performed within the time frame defined in the SoA.
- The type, amount (number of fingertip units), and frequency of topical products (see also [Section 6.5](#)) used during the study will be recorded in a medication log. The medication log might look different for AD patients and healthy volunteers.
- The maximum amount of blood collected from each participant over the duration of the study, including any extra assessments that may be required, will not exceed 50 mL. Repeat or unscheduled samples may be taken for safety reasons or for technical issues with the samples.
- In light of the public health emergency related to COVID-19 (or in case of any other public health emergency), the continuity of clinical study conduct and oversight may require implementation of temporary or alternative mechanisms, such as phone contact, virtual visits, online meetings, use of local clinic or laboratory locations, and home visits by skilled staff. Implementation of such mechanisms may differ country by country, depending on country regulations and local business continuity plans. Additionally, no waivers to deviate from protocol enrollment criteria due to COVID-19 (or any other pandemic) will be granted. All temporary mechanisms utilized, and deviations from planned study procedures are to be documented as being related to COVID-19 (or any other public health emergency) and will remain in effect only for the duration of the public health emergency.

8.1 PROCEDURES PERFORMED ONLY AT THE SCREENING/BASELINE VISIT

Assessments performed only at the screening and/or baseline visit include medical history, medication history, IGA, demographics, and diagnosis of chronic AD. AD disease characteristics are assessed by clinical and patient reported outcomes.

8.2 EFFICACY ASSESSMENTS

8.2.1 Transepidermal water loss assessment and skin tape stripping

8.2.1.1 Transepidermal water loss assessment

Transepidermal water loss is a skin barrier function test that measures perspiration or water loss through the skin. Transepidermal water loss is generally higher in AD skin compared to normal skin as the barrier is disrupted allowing water to evaporate more readily. If the barrier improves with dupilumab treatment, TEWL would be expected to decrease.

TEWL assessment will be conducted in a quiet environment with temperature and humidity being documented. TEWL measurements will be conducted in the same room throughout the study where possible. Subjects will be acclimated to the room for a minimum of 20 minutes prior to TEWL measurements. Room temperature will be set to be within 19.0°C to 23.0°C. Humidity will be set to be below 60% as the maximum allowed humidity. To further control TEWL readout, moisturizers will be standardized for all study participants starting from Day -7 until Day 113 (Week 16). The first TEWL assessment at each visit will be conducted at each of the three spots in predefined lesional and non-lesional areas respectively. After start of STS all subsequent TEWL assessments at each visit will be done on the single lesional and non-lesional spot respectively at which the STS is performed (see also [Figure 3](#)).

8.2.1.2 Skin tape stripping and collection of skin tapes

In addition to TEWL measurements at the skin surface, TEWL measurements can be combined with STS to measure skin barrier function. With STS, the uppermost layers of the skin are peeled away using adhesive discs. Skin with compromised skin barrier exhibits greater changes in TEWL. The area under the curve for TEWL measurements over a defined number of STS reflects the overall function of the SC.

This procedure involves the defined, non-invasive application of a commercially available adhesive sheet on the surface of the skin at predefined areas. A dedicated instrument (eg, D-SQUAME Pressure Instrument D500) is used to apply a defined pressure onto the skin tape strip for 5 to 10 seconds. Thereafter the skin tape strip will be peeled off the skin in a ripping motion using a forceps (= the skin tape-stripping method).

This procedure will be repeated up to 20 times sequentially, interrupted every 5 STS by TEWL to collect samples from the stratum corneum. The samples will be collected for lipidomics, proteomics and transcriptomics assessment.

[figure not shown]
Lesional and non-lesional areas of skin will be tested. Patients will undergo skin barrier function tests at time points according to [Section 1.3](#) before, and after skin tape stripping.

Healthy volunteers will undergo skin barrier function tests at time points according to [Section 1.4](#) before, and after skin tape stripping.

Specifically, lipidomic, proteomic and transcriptomics samples will be collected by STS at baseline, Week 2, 4, 8, 12, and 16. A total 240 skin tapes will be collected in lesional, non-lesional or normal skin, respectively.

[figure not shown]
In order to allow the skin to recover from STS three closely adjacent spots (without an overlap for the skin tapes) will be identified for subsequent skin barrier function assessment within lesional, non-lesional and normal skin area ([Figure 2](#)). STS assessments from the same spot will be separated by 8 weeks. In case of STS assessment at an unscheduled visit or at a premature end of treatment visit the assessment should be conducted at that spot of the skin area, for which the time period passed since the last STS assessment is the longest.

Figure 2 - Example of selection of skin spots within lesional and non-lesional skin

TEWL assessment in lesional, non-lesional and normal skin will be done before, and after skin tape stripping according to the attached [Figure 3](#). All skin tape strips will be collected, stored, and analyzed for lipidomics, proteomics and transcriptomics according to [Section 8.9](#).

Figure 3 - TEWL assessment and STS in lesional and non-lesional skin of AD patients and in normal skin of HV

The detailed procedure for TEWL, skin tape stripping, collecting and storing skin tapes for lipidomic, proteomic and transcriptomic analysis will be provided in the study reference manual. Details about lipidomic, proteomic and transcriptomic analyses by time point will be provided in the SAP.

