- g* Peak pruritus NRS and quality of sleep NRS will be assessed daily from Day-7 to Day -1; daily from Day 1 to Day 29 and then for the 7 days prior to Week 6, Week 8, to Week 12 and to Week 16 by e-diary. Patients will bring the eDiary to the site at each visit. eDiary will be reviewed for any questionnaires omission and dispensed back to patients at each visit.
- h* TEWL to be conducted before STS and then after 5, 10, 15, and 20 STS in pre-defined lesional and non-lesional skin. All skin tape strips will be collected and stored.
- i* At Week 0, 8 and 16 STS will be conducted on the first spot within the predefined skin area. At Week 2 STS will be conducted on the second spot within the predefined skin area. At Week 4 and 12 STS will be conducted on the third spot within the predefined skin area. TEWL will be assessed in lesional and non-lesional skin before STS and after 5, 10, 15, and 20 STS. All skin tape strips will be collected and stored for lipidomics, proteomics, and transcriptomics analyses.
- j* Emollients should NOT be applied from Day -7 to the EoT (Week 16, Day 113) to the targeted, pre-defined skin areas that will be used for TEWL assessment. Participants should not take showers or soaking in a bathtub within 6 hours before TEWL assessment. Compliance must be documented in participant's source data. Emollients for use during the study will be provided by the study site to study participants. Use of emollients should be documented in a diary.
- k* Limited to skin-related physical examination at baseline and EoT visit.
- l* Pre-defined lesional (3 spots) and non-lesional skin areas (3 spots), whereby the assessment spots on non-lesional skin are located about 4 cm apart from the edge of the AD lesion.
- m* TEWL will be measured at each of the three closely adjacent spots within the predefined skin areas at all visits as baseline assessment; if there is STS, subsequent TEWL assessment will only be done at the lesional and no-lesional spot, at which STS is performed.
- n* In case STS assessment is to be conducted at an unscheduled visit or at a premature end of treatment visit the assessment should be conducted at that spot of the skin area, for which the period passed since the last STS assessment is the longest.

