1.3 DATA HANDLING CONVENTIONS

This section describes the rules and conventions used in the presentation and analysis of data.

In the statistical appendices and in-text tables, the following cohort label and group label will be used:

- Cohort label:
 - AD patients
 - Healthy volunteers
- Group label:
 - AD patients – lesional skin
 - AD patients – non-lesional skin
 - HV – healthy skin

For parameters with evaluations before administration and in cases of rechecked value(s) for one subject, only the last observation will be used as baseline in descriptive statistics and derivations of other parameter values. After baseline, only observations planned in the protocol will be used in descriptive statistics.

If not otherwise stated in the statistical section of the protocol:

- Missing TEWL data (including data from visits excluded of the efficacy analyses after the use of prohibited medication) will be imputed using Last Observation Carried Forward (LOCF) imputation ; sensitivity analyses will be performed to assess the precision of LOCF imputation versus MMRM imputation.
- Descriptive statistics for quantitative parameters will be provided using number of observations (N), mean, standard deviation (SD), standard error of the mean (SEM), minimum, maximum and median.
- Descriptive statistics for qualitative parameters will be provided using frequencies (N) and percent (%).

Handling missing data for adverse events

In case of missing or inconsistent information on the time of onset, an AE will be counted as a treatment-emergent adverse event (TEAE) unless it can clearly be ruled out that it is not a TEAE (eg, by partial dates or other information).

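### Before Week 8 the spot rule for off-schedule tape stripping cannot be met together with the 8-week same-spot separation, and it may bias the next planned after-stripping readings

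*Protocol*

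**What the plan says.** Each lesional, non-lesional or normal skin area has three adjacent spots. Footnote i of the AD schedule (Protocol 1.3) states "At Week 0, 8 and 16 STS will be conducted on the first spot within the predefined skin area"; it assigns Week 2 to the second spot and Weeks 4 and 12 to the third. Protocol 8.2.1.2 gives skin recovery as the purpose and says "STS assessments from the same spot will be separated by 8 weeks".

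The next sentence of 8.2.1.2 covers off-schedule stripping: use the spot "for which the time period passed since the last STS assessment is the longest". Footnote n of the AD schedule repeats this for the case "In case STS assessment is to be conducted at an unscheduled visit or at a premature end of treatment visit", and footnote j of the healthy-volunteer schedule (Protocol 1.4) says the same. Both schedules mark after-STS TEWL and tape sampling with a plain X at premature end of treatment and a bracketed X at unscheduled visits.

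Three other provisions bear on this:

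- After definitive discontinuation of study drug, "the participant will remain in the study to be evaluated for TEWL, lipidomics, proteomics and transcriptomics" (Protocol 7.1.1).
- Before rescue treatment, investigators should try to complete assessments first: "An unscheduled visit may be used for this, if necessary" (Protocol 6.5.1).
- SAP 1.3 states "After baseline, only observations planned in the protocol will be used in descriptive statistics". It has no rule for a planned reading taken on a spot that was recently stripped off schedule.

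**The concern.** The off-schedule rule looks only backwards. It asks how long ago a spot was stripped, not when it is due again. Before Week 8 the spot it selects still has a planned stripping ahead, so the extra procedure shortens the recovery time that the three-spot layout was meant to protect.

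At stake are the planned after-STS TEWL, TEWL AUC and tape samples at Week 2, 4 or 8. Week 8 is a named time point for the lipidomics endpoint and for the TEWL correlations (Protocol Section 3, Table 1). Extra visits are also unlikely to be a random sample: they would tend to come from patients who flare or stop drug. With about 20 evaluable patients, one affected patient carries 1/20 = 5% of a group mean.

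**Working it through.** **Inputs.** Nominal STS days are 1, 15, 29, 57, 85 and 113 (Protocol 1.1, overall design). Spot 1: Days 1, 57, 113. Spot 2: Day 15. Spot 3: Days 29, 85. Required separation: 8 × 7 = 56 days.

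**Step 1: reproduce the plan's figure.** Spot 1: 57 − 1 = 56 and 113 − 57 = 56. Spot 3: 85 − 29 = 56. The planned schedule meets the rule on nominal days. With the visit windows (±2 days at Week 4; ±3 at Weeks 8, 12 and 16) these gaps become 53–59, 50–62 and 51–61 days.

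**Step 2: apply the off-schedule rule to one extra STS on day d.** The text does not say how to treat a never-stripped spot, so two readings are needed. Under A it counts as longest. Under B only spots with an earlier STS are compared. Days to the next planned STS = next planned day − d.

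| Day d | A: spot | A: days to next planned STS | B: spot | B: days to next planned STS |
|---|---|---|---|---|
| 2–14 | 2 or 3 (tie) | 15 − d = 1–13 (Week 2), or 29 − d = 15–27 (Week 4) | 1 | 57 − d = 43–55 (Week 8) |
| 16–28 | 3 | 29 − d = 1–13 (Week 4) | 1 | 57 − d = 29–41 (Week 8) |
| 30–56 | 1 | 57 − d = 1–27 (Week 8) | 1 | 57 − d = 1–27 (Week 8) |
| 58–84 | 2 | none planned | 2 | none planned |
| 86–112 | 2 | none planned | 2 | none planned |

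Before Week 8 the range is 1–27 days under A and 1–55 days under B, always below 56. Visit windows can stretch reading A to 32 days (Week 4 held on Day 27, extra STS on Day 28, Week 8 held on Day 60: 60 − 28 = 32).

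**Step 3: an example that does not depend on the reading.** On Day 50, spot 1 was stripped 49 days ago, spot 2 35 days ago and spot 3 21 days ago. The rule picks spot 1, due again in 57 − 50 = 7 days, although spot 2 has no further planned STS.

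**Step 4: after Week 8.** Spot 2 has nothing planned after Day 15, so a single extra STS there endangers no planned reading. On Days 58–70, however, it comes only 58 − 15 = 43 to 70 − 15 = 55 days after the Day 15 stripping. Day 71 is the first day on which any spot has 56 days clear in both directions (71 − 15 = 56).

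**Step 5: reach to the primary endpoint.** Baseline and Week 16 are both on spot 1. A single extra STS before Week 8 leaves the planned Day 57 and Day 113 strippings 56 days apart. A second extra STS can get closer: one on Day 90 goes to spot 2, then one on Day 100 goes to spot 1, 113 − 100 = 13 days before Week 16. The other route is last observation carried forward (SAP 1.3), if an affected earlier value stands in for a missing Week 16 value.

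**The case against.** The best defence is that the off-schedule sentence is a specific rule for exceptional visits and the 8-week sentence describes only the planned spots. That reading is possible, but nothing in the text calls the one an exception to the other. The Day 50 example also shows a poor result even as an exception, because it uses a spot with a planned reading ahead when another has none.

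Several limiting points stand:

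- Unscheduled STS is optional, Protocol 7.1.1 expects definitive discontinuation to be rare, and no frequency is given. A participant who withdraws from the study (Protocol 7.2) has no later planned reading to affect.
- The examples of pre-rescue assessments in Protocol 6.5.1 are severity scores and safety labs, not STS. If rescue is judged to affect the skin barrier significantly, the mITT analysis keeps only earlier visits (Protocol 9.3, Table 3). The ITT analysis retains the later ones, so this protection is partial.
- The SAP restriction to planned observations concerns descriptive statistics. A reader might infer that off-schedule data are never used. The documents do not support that: individual-value graphics are planned (Protocol 9.4.7), biomarkers have a separate SAP (Protocol Section 9), and premature end of treatment, with its own schedule column, is arguably a planned visit.

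A reader might also infer that the next planned reading is spoiled. The documents give a recovery rationale but no recovery time or carry-over size, so possible bias is as far as they go.

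**Conclusion.** The two rules cannot both be met before Week 8, and this holds under either reading of a never-stripped spot. The shortfall is large: the next planned STS on the chosen spot is 1–27 days away (reading A, the more natural one) or 1–55 days away (reading B), against a stated 56. These figures assume nominal days and one extra STS. The consequence arises only in participants who continue scheduled STS, including those who stop drug but stay in the study.

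Three stronger conclusions are tempting and should not be drawn. The 1–27 day range is not universal, because it depends on reading A and on nominal days. The primary Week 16 result is not directly affected by a single extra STS; it could be reached only by carrying forward an affected value or by repeated extra STS. Nor is the rule free of conflict after Day 57, given the 43–55 day gap on spot 2 on Days 58–70.

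What remains is a possible, probably selective bias of unknown size in secondary and exploratory Week 2, 4 and 8 data. It should be corrected because the current rule creates an avoidable problem and the repair is small.

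**What to change.** Reconcile the two sentences in Protocol 8.2.1.2, footnotes n and j, and the unscheduled and premature end-of-treatment STS cells in both schedules of activities:

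1. Participants who will continue scheduled STS have pre-STS TEWL only, with no stripping, at extra visits before Week 8.
2. From Week 8, one extra STS uses spot 2. State openly that on Days 58–70 this falls 43–55 days after the Day 15 stripping. Allow no second extra STS that would fall within 8 weeks of another STS on the same spot.
3. Participants leaving the study keep the longest-since-last-STS rule, with a never-stripped spot counted as longest.
4. In the SAP, flag any planned after-STS reading that follows an extra STS on the same spot by less than 8 weeks, and repeat the affected summaries without it. The extra STS must trigger the flag; otherwise ordinary visit windows, which already allow 50 days between planned strippings, would set it off.

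The cost is a few sentences, two footnotes, the schedule cells and one SAP flag. The scientific price is the loss of tape samples and after-STS TEWL at some extra visits before Week 8. Sites must also judge who will continue: a participant expected to stay who later drops out would have no sample from the time of stopping.
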